### **Objective and methods**

To study levels of biomarkers and epigenetic markers in blood in patients with symptomatic paroxysmal AF (n=100), in relation to severity of AF symptoms, and compared to age- and sex-matched controls without AF (n=100). Blood will be obtained before and after AF ablation and levels of biomarkers, epigenetic markers and cardiac and inflammatory markers, analysed. Patients will complete an AF-specific symptom and a generic health-related quality of life questionnaire.

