### **Epigenetic markers**

Epigenetic mechanisms such as DNA methylation, covalent histone modifications, and non-coding RNAs, have been observed to play an important role as mediators of long-term changes in central and peripheral nervous systems in chronic pain. Epigenetic markers can be measured in blood or tissue(36-37). To our knowledge, pain-related epigenetic markers have not been analysed in patients with AF.

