### ***Blood samples***

Blood samples for biomarkers and epigenetic markers associated with pain, cardiac biomarkers, and inflammatory markers, will be obtained when standard blood samples are taken the day before the ablation, and the day after ablation. In total 30 ml of blood per time will be obtained. In controls, the same blood samples will be obtained once only. Blood

samples will be stored in a biobank for possible later analysis. Blood samples may be analysed in another laboratory in Sweden or in the EU/ESS.

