### ***Statistical analysis***

Data will be presented as mean and standard deviation. Independent t-test will be used to compare biomarkers and epigenetic markers in AF patients and control subjects. Pearson correlations will be used for linear estimates and Spearman's correlations for non-linear parameters. Multiple linear regression analysis will be performed to show associations between explanatory variables (age, sex, symptoms) and biomarkers and epigenetic markers associated with pain. Analyses will be performed using IBM SPSS Statistics 22 (Armonk, NY, USA) or STATA release 14 (College Station, TX, USA).

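### If the epigenetic markers are measured in blood cells, the planned t-test and symptom regression cannot separate an epigenetic difference from a difference in white-cell proportions

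*Combined protocol and SAP*

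**What the plan says.** The Statistical analysis section gives two relevant analyses. The group comparison is "Independent t-test will be used to compare biomarkers and epigenetic markers in AF patients and control subjects", which takes no covariates. The multiple linear regression is to show "associations between explanatory variables (age, sex, symptoms) and biomarkers and epigenetic markers associated with pain". Pearson and Spearman correlations are also planned, again without covariates.

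On the specimen, the Blood samples section says "Blood samples for biomarkers and epigenetic markers associated with pain, cardiac biomarkers, and inflammatory markers, will be obtained", without naming the fraction (whole blood, separated cells, plasma or serum). Patients are sampled before and after the procedure: samples "will be obtained when standard blood samples are taken the day before the ablation, and the day after ablation". Controls are sampled once.

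On the marker, the Epigenetic markers section of the Introduction gives DNA methylation, histone modification and non-coding RNA as examples of mechanisms, and says "Epigenetic markers can be measured in blood or tissue". The methods fix no particular marker or assay.

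The Control group section matches on sex and age and recruits by advertisement. The Primary endpoint section places epigenetic markers in both primary objectives. Inflammatory markers are measured but not named, and they are not listed among the explanatory variables of any model.

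**The concern.** Blood contains several kinds of white cell, and their epigenetic profiles can differ. A methylation, histone or cellular RNA level measured in mixed blood cells is then partly a readout of which cells were in the tube. If patients and controls differ in neutrophil or lymphocyte share, or if that share varies with symptom severity, the measured level shifts even when no cell of any type has changed.

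Matching on age and sex does not balance this, and neither analysis contains a term that could absorb it. A positive result on either primary objective would then have a rival explanation that the planned analysis cannot examine. The second hypothesis would read raised levels in patients as support for central sensitisation, so the distinction matters for interpretation. Cell mix also adds variance that can hide a real difference.

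**Working it through.** The plan gives no alpha, power, effect size or SD, so there is no figure of its own to reproduce. Only the group sizes, 100 and 100 (Objective and methods), come from the documents. Everything else below is an assumption, shown as a range.

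**Group comparison.** The true AF effect is set to zero.

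- D, difference in methylation between neutrophils and other white cells: 0.1, 0.2 or 0.5
- between-person SD of neutrophil fraction: 0.08
- s, SD of the marker from all other sources: 0.02 or 0.05
- shift in mean neutrophil fraction between groups: 0.02 or 0.05
- two-sided alpha: 5%

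Formulas: total SD = sqrt((D × 0.08)² + s²); standardised shift = D × shift / total SD; noncentrality = standardised shift / sqrt(2/100), entered in a noncentral t with 198 df; share of variance due to cell mix = (D × 0.08)² / total SD².

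Worked case, D = 0.2 and s = 0.02: total SD = sqrt(0.016² + 0.02²) = 0.0256. A 2-point shift moves the mean by 0.2 × 0.02 = 0.004, which is 0.16 SD. The noncentrality is 1.10 and the rejection rate 20%.

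| D | s | Cell mix, share of variance | False positives, 2-point shift | False positives, 5-point shift |
|---|---|---|---|---|
| 0.1 | 0.05 | 2.5% | 5.9% | 10.7% |
| 0.2 | 0.05 | 9% | 8.4% | 26.8% |
| 0.1 | 0.02 | 14% | 10.0% | 37.2% |
| 0.2 | 0.02 | 39% | 20% | 78% |
| 0.5 | 0.05 | 39% | 20% | 78% |
| 0.5 | 0.02 | 80% | 35% | 98% |

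On the assumed SD of 0.08, a 2-point shift is 0.02/0.08 = 0.25 SD of neutrophil fraction and a 5-point shift is 0.05/0.08 = 0.63 SD. With D = 0 the rate stays at 5%.

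**Cross-check in standardised units.** Let r be the correlation of marker with cell share and d the group difference in cell share in SDs. The spurious difference is r × d. Rates are 9.7% (r = 0.3, d = 0.3), 18.4% (0.5, 0.3), 42.1% (0.5, 0.5) and 69.2% (0.7, 0.5). In 4,000 simulated studies per case, adding cell share as a covariate returned the rate to 4.8-5.2%.

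**Symptom regression.** This was simulated with 100 patients and a true symptom effect of zero, in a model of marker on age, sex and symptoms, where cell share correlates q with symptoms.

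| r | q | As planned | With cell share added |
|---|---|---|---|
| 0.3 | 0.2 | 8.3% | 4.6% |
| 0.5 | 0.2 | 16.8% | 4.9% |
| 0.5 | 0.3 | 30.8% | 4.6% |
| 0.7 | 0.3 | 55.3% | 5.2% |

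The adjusted rates assume that cell share is measured without error and acts as a confounder.

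**The case against.** Several objections have force.

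- **The marker may not be cellular.** The mechanisms appear in background text as examples and include non-coding RNA, and the fraction is not stated. Cell-free RNA in plasma or serum would largely escape this problem. This stands and makes the point conditional. It does not remove it, since nothing in the plan excludes white-cell markers.
- **A count may already exist.** Study blood is drawn with the standard samples, whose content is not listed, and the inflammatory panel is unnamed. A reader might infer that no differential is taken. The documents support only that none is specified and none enters a model.
- **The day-after sample.** A reader might infer that a before-after comparison is confounded by a cell response to the procedure, the more so because the protocol describes epigenetic mechanisms as "mediators of long-term changes in central and peripheral nervous systems in chronic pain". But the Statistical analysis section states no before-after analysis and does not say which patient sample enters the t-test. The argument would apply only if such a comparison were made.
- **The high false-positive rates are a corner of the range.** Rates of 78-98% need a 5-point group shift and either a strongly cell-discriminating marker or little other variation. Nothing in the documents points to a shift of that size. With D = 0.1 and s = 0.05 the rates are 5.9% and 10.7%.
- **Cell mix may lie on the causal path.** If AF or its symptoms alter white-cell proportions, the adjusted and unadjusted results answer different questions. This stands, and it is a reason to report both and not to rely on the adjusted model alone.

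**Conclusion.** The point holds conditionally. For epigenetic markers measured in blood cells, neither the t-test nor the regression on age, sex and symptoms can tell an epigenetic difference from a difference in white-cell proportions. The matching does not help, and the plan specifies no measurement of those proportions.

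The size of the bias cannot be derived from the documents. Under the assumptions above, a 2-point group shift in neutrophil fraction gives about 6-35% false positives and a 5-point shift about 11-98%, with cell mix forming about 2.5-80% of marker variance. A marker that does not differ by cell type, or cell-free RNA in plasma or serum, is largely unaffected. The documents do not show that patients and controls actually differ in cell mix, only that the analysis could not detect it if they did. The correction is worth making because it is cheap and because both primary objectives include these markers.

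**What to change.** State the epigenetic marker and the blood fraction. For any marker measured in blood cells:

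1. Obtain a white-cell differential on the same draw in patients and controls. Use the routine result where one exists, or estimate proportions from the methylation data if an array is used.
2. In the Statistical analysis section, add a regression version of the patient-control comparison with neutrophil and lymphocyte proportions as covariates.
3. Add the same covariates to the symptom regression, and to any before-after comparison if one is made.
4. Report results with and without this adjustment, and describe a difference as independent of cell mix only if it persists after adjustment.

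Cost: at most about 300 routine counts (100 patients × 2 draws + 100 controls × 1 draw), fewer where results already exist; one or two degrees of freedom per model; and a few sentences in the plan. The text should also say that the two sets of results answer different questions if AF or symptoms themselves change white-cell proportions.

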### ***Database and Case report form***

A case report form will be filled out and coded for each patient. The investigators are responsible for ensuring the accuracy, completeness, legibility and timeliness of the data recorded in the case report forms.

### ***Documentation and data collection***

Criteria for inclusion, informed consent, the decision to include the subject and the subject number will be documented in the subject's hospital record.

### ***Insurance***

The subjects in the study are covered by the Swedish patient insurances.

### ***Economy***

The trial is an academic study conceived and conducted by healthcare personnel. The study is independent of commercial interests. Study logistics, handling of data and statistical assessment will be financed by the Department of Cardiology, Örebro University Hospital, Sweden. The investigators will apply for grants from public funds. Neither patients nor controls will receive economic compensation.

## **Ethical considerations**

The study will be conducted in accordance with the Declaration of Helsinki. The protocol is submitted to the Swedish Ethical Review Authority and the study will be initiated when the protocol has been approved. There are no known risks or complications associated with additional blood samples in association with standard blood samples being obtained, but it may cause some temporary discomfort.

### ***Risks, side effects, advantages and disadvantages in participation***

Subjects will be treated according to standard clinical practice. We do not expect that subjects will have any advantages or disadvantages from participating in the study.

### ***Guidelines for obtaining informed consent***

Subjects will enter the study after signing the informed consent form. Candidate participants will receive written information of the study, and oral information by a physician participating in the study. The subjects will be given time to think through participation in the study and to ask questions. Informed consent will be obtained by a Good Clinical Practice qualified physician participating in the study.

### ***Withdrawal***

A subject can withdraw from the study at any time. Data collected up to the end of follow-up will be used in the final analysis of the study.

## **Publication**

Results, positive as well as negative or inconclusive, will be published in an international medical journal.

### **End of trial and archiving**

The study will end when the last subject has signed informed consent, completed the questionnaires and has undergone clinical examination and had blood samples taken. The steering committee reserves the right to terminate the study prematurely e.g. if the study participant recruitment is too slow, if study participant retention in the study is insufficient. Data collected during the study will be archived for at least 10 years after the study has been completed.

